11.2.1 Efficacy analysis

Kaplan–Meier survival analysis was performed to assess weaning and survival outcomes.

Mann Whitney test was used for compare non-parametric data (weaning rate, length of ventilator use, length of ICU stay and length of hospitalization).

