comparisons, one-way analysis of variance (ANOVA) followed by Dunnett's test, where appropriate, was used to determine the statistical significance of the difference between means. The follow-up parametric data were compared using the paired student's t-test. Non-parametric data were determined by chi-squared tests. Analyses of primary and secondary outcomes are performed with the use of time-to-event methods according to the intention-to-treat principle. All analyses were two-sided, and $p<0.05$ was considered statistically significant. Statistical analyses were performed using Prism version 5 (GraphPad Software Inc., La Jolla, CA, USA).

5. Handling of Missing Data :

Omit the cases with missing data and analyze the remaining data.

2. Introduction and Rationale

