2.5 Regulatory

This study will be conducted in compliance with the protocol approved by the Institutional Review Board, and according to Good Clinical Practice standards. No deviation from the protocol will be implemented without the prior review and approval of the IRB except where

it may be necessary to eliminate an immediate hazard to a research subject. In such case, the deviation will be reported to the IRB as soon as possible.

3. Objectives and Endpoints

3.1 Study Objectives:

3.1.1 Primary objective:

To evaluate the benefit of high protein supplementation and core muscle rehabilitation and trunk NMES intervention in weaning from ventilator

3.1.2 Secondary objectives:

The impact of renal function and digestion status after high protein intake
The benefit in nutrition status and diaphragm weakness and the correlation to weaning status

3.1.3 Other exploratory objectives (if any):

1.2 Study endpoints:

3.2.1 Primary endpoint:

Weaning rate

(weaning success defined as weaning from ventilator for 5 consecutive days)

3.2.2 Secondary endpoints:

In hospital mortality, Length of mechanical ventilator usage,
Length of ICU stay and total length of hospitalization,
Serum albumin level improvement, Creatinine clearance rate

3.2.3 Other exploratory endpoints (if any):

4. Study Design

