11.2 Planned Statistical methods of analysis

Categorical variables were expressed as count and percentage. Parametric data were expressed as mean \pm standard deviation (SD). A Student's t-test was used to compare parametric data. Fisher's exact test was used to compare non-parametric data. We used a receiver operating characteristic (ROC) curve to identify the optimal cut-off-value for the maximum multiplication of sensitivity and specificity. Logistic regression was used for multivariate analysis. Kaplan–Meier survival analysis was performed to assess weaning and survival outcomes. Statistical significance was set at a p-value < 0.05 . Statistical analyses were performed using GraphPad Prism version 8 (GraphPad Software, La Jolla, CA, USA) and IBM SPSS Statistics 26 (SPSS, Chicago, IL, USA).

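### Kaplan–Meier is planned for weaning with no rule for death before weaning; under the usual censoring at death, weaning is overstated in any arm where a death precedes a later weaning

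*Combined protocol and SAP*

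**What the plan says.** The primary endpoint in section 3.2.1 is the weaning rate, with "weaning success defined as weaning from ventilator for 5 consecutive days". The definition fixes no day by which this must happen. The secondary endpoints in section 3.2.2 begin with "In hospital mortality, Length of mechanical ventilator usage", so the plan allows for patients dying during follow-up.

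Several methods could apply to weaning:

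- Sections 11.2 and 11.2.1: "Kaplan–Meier survival analysis was performed to assess weaning and survival outcomes".
- Section 11.2.1, next sentence: "Mann Whitney test was used for compare non-parametric data (weaning rate, length of ventilator use, length of ICU stay and length of hospitalization".
- Section 11.2: "Fisher's exact test was used to compare non-parametric data" and "Logistic regression was used for multivariate analysis", the latter without naming an outcome.
- Synopsis, Statistical Methods: "Analyses of primary and secondary outcomes are performed with the use of time-to-event methods according to the intention-to-treat principle", and also "Non-parametric data were determined by chi-squared tests".

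None of these is named as the primary analysis. No section gives a censoring rule, names a competing-risk method, or says that a patient who dies on the ventilator counts as not weaned. Section 11.3 takes everyone randomised as the analysis population. The missing-data rules in the synopsis and section 11.4 remove incomplete cases without saying whether a death makes a case incomplete. Section 5.3 lists return to ICU among the withdrawal criteria and does not say how these patients enter the weaning analysis.

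**The concern.** A Kaplan–Meier curve recognises only an event or a censored time. A patient who dies on the ventilator can no longer wean. Censoring that patient at death lets the patients still at risk stand in for them, as though they would later have weaned at the same rate. One minus the curve then describes a setting in which nobody dies before weaning. It does not give the share of randomised patients who come off the ventilator, which is what a weaning rate is normally taken to mean.

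Two consequences bear on the primary endpoint. The reported level is too high wherever a death is followed by a later weaning. The size of the error depends on each arm's mortality, so arms with different mortality are distorted by different amounts. Because the plan does not state the rule, the choice could also be made after the data have been seen.

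**Working it through.** **Inputs.** The only design figure in the documents is the sample size. It reproduces as 10 + 3 × 30 = 100 (section 11.1), but it does not bear on this point. No weaning rate, death rate or power is stated, so every rate below is an assumption, shown over a range.

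**1. Size of the overstatement.** Let w be the true proportion weaned by the horizon and d the proportion dying before weaning, with constant cause-specific hazards.

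- Total cumulative hazard: H = −ln(1 − w − d)
- Weaning share of it: Hw = H × w/(w + d)
- Kaplan–Meier weaning figure with deaths censored: 1 − exp(−Hw)
- Cumulative incidence of weaning: w

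With w = 50%:

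| d | H | Hw | Kaplan–Meier reads | Excess (points) |
|---|---|---|---|---|
| 5% | 0.799 | 0.726 | 51.6% | 1.6 |
| 10% | 0.916 | 0.764 | 53.4% | 3.4 |
| 20% | 1.204 | 0.860 | 57.7% | 7.7 |
| 30% | 1.609 | 1.006 | 63.4% | 13.4 |

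For the same four values of d, the excess is 1.2, 2.6, 5.7 and 9.7 points if 40% truly wean, and 2.1, 4.4, 10.1 and 18.5 points if 60% do. With no deaths before weaning it is zero.

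**2. Masking.** Give two arms the same cumulative weaning hazard, Hw = 0.70, and cumulative death hazards Hd of 0.2 and 0.6.

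- Kaplan–Meier in both arms: 1 − exp(−0.70) = 50.3%
- Truly weaned, first arm: (0.70/0.90) × (1 − exp(−0.90)) = 46.2%, with 13.2% dying first
- Truly weaned, second arm: (0.70/1.30) × (1 − exp(−1.30)) = 39.2%, with 33.6% dying first

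A difference of 46.2 − 39.2 = 7.0 points does not appear in the Kaplan–Meier figures. Similarly, two arms that both read 60%, with 10% and 30% dying first, truly wean 56.0% and 47.6%, a gap of 8.4 points.

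**3. Effect of the remedy.** In 3,000 simulated arms of 30 patients with w = 50% and d = 20%, the mean weaning figure was 57.9% with deaths censored at death. It was 50.2% with deaths kept in the risk set to day 28, equal to the crude proportion of 50.2%.

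**4. Whether a crude proportion is safe as the plan stands.** Only if deaths stay in the denominator. With w = 50% and d = 20%, removing deaths as incomplete cases would give 50/(100 − 20) = 62.5%, further from the truth than the Kaplan–Meier figure.

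**The case against.** The strongest reply is that the plan names Kaplan–Meier but never says that deaths are censored. Deaths carried to day 28 as not weaned can also be put through Kaplan–Meier, and the bias then disappears. This stands: a reader might infer that the plan prescribes censoring at death, but that is the usual convention and not a written rule. What remains is that the convention applies unless something else is specified, and nothing else is.

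A reader might also infer that weaning would be overstated in every arm. That does not follow. An arm with no death before a later weaning is unaffected. In the 10-patient usual-care arm, the chance of no death before weaning is 0.95^10 = 60%, 0.90^10 = 35%, 0.80^10 = 11% and 0.70^10 = 3% at risks of 5%, 10%, 20% and 30%. This gives limited reassurance, because a bias present in the treated arms and absent in the comparator still distorts the contrast.

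Nor is Kaplan–Meier the only planned analysis of weaning. Mann–Whitney is assigned to the weaning rate, Fisher's exact and chi-squared tests are listed generally, and the population is everyone randomised. A proportion on that denominator is free of this bias, but the plan neither commits to it nor protects it from the missing-data rules. The synopsis does not mention Kaplan–Meier at all, and its time-to-event wording would already admit cumulative incidence.

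On size, eligible patients must be clinically stable and the schedule ends at day 28 ± 1, so low death risks are plausible. At 5% or 10% the excess around 50% weaning is 1.6 or 3.4 points, against binomial standard errors of about 9 points for 30 patients (√(0.25/30)) and 16 points for 10 (√(0.25/10)). Section 11.1 also calls the study exploratory. Both points temper the urgency, but neither makes the estimate the right quantity. Finally, a mortality difference would still show in the separate mortality and survival analyses. What can be masked is its effect on weaning.

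**Conclusion.** The concern holds in conditional form. The plan applies Kaplan–Meier to weaning without a rule for death before weaning. Followed in its usual form, it overstates weaning in any arm where a death precedes a later weaning, and it can mask an arm difference in weaning that arises from deaths. With 50% truly weaned, the excess runs from 1.6 points at 5% deaths to 13.4 points at 30%. These figures rest on constant hazards and assumed rates, and the documents do not show where in the range the trial will fall. The documents do not support the stronger readings that deaths will certainly be censored, that every arm is affected, or that the primary endpoint has no other planned analysis.

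**What to change.** - **Sections 11.2 and 11.2.1:** for weaning, replace Kaplan–Meier by the cumulative incidence function with death before weaning as a competing event. Equivalently, with complete follow-up, keep deaths in the risk set as never weaned to a fixed day, such as the scheduled day 28. Kaplan–Meier can remain for survival.
- **Synopsis:** make the general time-to-event wording match.
- **Horizon:** state the day, and whether the event is dated at the first or the fifth ventilator-free day. A patient who comes off on day 26 completes five days only on day 30.
- **Proportion weaned:** state that the denominator is all randomised patients, with deaths before weaning counted as not weaned and not removed under the missing-data rules in the synopsis and section 11.4.
- **Withdrawals under section 5.3:** keep recording weaning and death for patients withdrawn on return to ICU, and do not censor them at withdrawal.
- **Primary analysis:** name one. A log-rank comparison with deaths censored may be reported as supportive, described as a comparison of weaning hazards.

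The cost is small: revised wording, one procedure in software that supports cumulative incidence, and slightly lower reported weaning rates. Mortality and ventilator duration are already in the schedule of activities. The only added data work is continued outcome recording for withdrawn patients, where the plan does not already intend it.

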6.1. Treatments Administration	
6.2. Concomitant Therapy	
7. Efficacy Assessments	
8. Safety Assessments	
9. Adverse Event reporting	
9.1. Definition and reports of Adverse Events.....	
9.2. Adverse event follow-up.....	
10. Criteria for the termination of the trials	
11. Statistical Considerations	

11.1.	Sample Size Determination
11.2.	Planned Statistical methods of analysis.....
11.2.1.	Efficacy analyses.....
11.2.2.	Safety analyses.....
11.2.3.	Additional analyses
11.2.4.	The level of significance
11.2.5.	Analysis Population
12.	Direct access to source data/documents
13.	Ethical considerations
14.	Data handling and keeping
15.	Financing and Insurance
16.	References.....

1. Synopsis

Protocol Title : The effects of high protein supplementation, core muscle rehabilitation and neuromuscular electrostimulation (NMES) on clinical outcomes in patients with prolonged mechanical ventilation (PMV)

Study Objectives :

To evaluate the benefit of high protein supplementation and core muscle rehabilitation and trunk NMES intervention for weaning in PMV patients.

Investigational product(s) :

high protein supplementation (1.5 g/kg/day protein)

core muscle rehabilitation (sitting for 30 minutes, twice per day, 5 days per week)

trunk NMES intervention (Electrodes were placed on back designed to activate latissimus dorsi and abdominal wall designed to activate the transversus abdominis and internal and external oblique muscles.

Electrical muscle stimulation was performed by using a using a commercial stimulator (GEMORE, GM300E, Taipei, Taiwan)

with biphasic waves at a simulation frequency of 30 Hz and pulse width of 400s, cycling 2s on and 4s off. Electrical muscle stimulation intensity was gradually increased until a visible muscle contraction was observed (median 60 mA [range 50–65 mA].)

Development Phase : I II III IV 其它 _____ 不適用

Study Design :

1. Experimental Group :

1. High protein supplementation
2. High protein supplementation + Core muscle rehabilitation
3. High protein supplementation + Core muscle rehabilitation + trunk NMES intervention

Control Group :

Usual care in Respiratory Care Center

2. Blinding : Open Evaluator-blind Single-blind(patient) Double-blind(patient+PI)
 Double Dummy Other _____

3. Randomization: Yes No

4. Parallel design Crossover design Other _____ Not applicable

5. Treatment Period : 3 weeks Not applicable

6. Study Period: 2 years

6. Dose adjustment : Mandatory Selectively No Not applicable

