11.2.4 The level of significance

A p-value less than 0.05 was considered significant and was denoted by * and p-value less than 0.01 was denoted by **.

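### Weaning, the primary endpoint, is assigned to several analyses, and the plan designates no single primary test or primary contrast among the four arms

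*Combined protocol and SAP*

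**What the plan says.** The primary endpoint (synopsis and section 3.2.1) is the weaning rate, with success meaning five consecutive days off the ventilator. No assessment day is given in that definition. The methods attached to it are:

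- **Synopsis, statistical methods:** "Analyses of primary and secondary outcomes are performed with the use of time-to-event methods according to the intention-to-treat principle". The same paragraph sends non-parametric data to chi-squared tests.
- **Section 11.2:** Kaplan-Meier for weaning. Non-parametric data go to Fisher's exact test.
- **Section 11.2.1, first sentence:** Kaplan-Meier again ("survival analysis was performed to assess weaning and survival outcomes").
- **Section 11.2.1, next sentence:** "Mann Whitney test was used for compare non-parametric data (weaning rate, length of ventilator use, length of ICU stay and length of hospitalization".

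There are four nested arms: usual care (UC); UC plus high protein; that plus core rehabilitation; and that plus NMES. The synopsis identifies the control group as "Usual care in Respiratory Care Center". The primary objective in section 3.1.1 is "To evaluate the benefit of high protein supplementation and core muscle rehabilitation and trunk NMES intervention in weaning from ventilator", which names no arm-against-arm comparison. The only multi-arm procedure, ANOVA followed by Dunnett in the synopsis, "was used to determine the statistical significance of the difference between means". Section 3.2.2 lists "In hospital mortality, Length of mechanical ventilator usage" among the secondary endpoints. Section 11.2.4 sets the threshold: "A p-value less than 0.05 was considered significant". Section 11.1 calls the study exploratory and sizes it by annual admissions.

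**The concern.** Three choices behind the primary conclusion are open. The first is the test: time-to-event, Mann-Whitney, chi-squared and Fisher's exact can each be justified from the text. The second is the rule for a patient who dies before weaning, which any time-to-weaning analysis needs. The third is the contrast: the whole package against UC, each arm against UC, or each added component against the step before it.

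These choices affect both the question answered and the chance of a significant result. If they are settled after the data are seen, a reader cannot tell whether the reported result was the planned one.

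**Working it through.** **The plan's own figure.** 10 UC + 3 × 30 = 100, as section 11.1 states. The plan gives no weaning rate, death rate, effect size or power, so every rate below is an assumption.

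**Number of contrasts.** Four arms give 4 × 3 / 2 = 6 pairs, of which three are against UC and three are adjacent steps.

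**Test choice, one invented result: 3/10 v 20/30 weaned.**
- Pooled rate 23/40 = 0.575; difference 0.667 − 0.300 = 0.367.
- Pearson chi-squared = 0.367² / [0.575 × 0.425 × (1/10 + 1/30)] = 0.1344 / 0.03258 = 4.13, p = 0.042.
- Mann-Whitney on 0/1 data (tie-corrected, no continuity correction) = 39/40 × 4.13 = 4.02, p = 0.045.
- Fisher's exact: p = 0.066.

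Tests named in the plan fall on both sides of 0.05.

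**Test choice, long run.** For 10 v 30 at an assumed 40% v 70% weaned, exact enumeration of all 11 × 31 outcomes gives 41% significant with Mann-Whitney and 29% with Fisher; they disagree in 12%. Log-rank, simulated with constant hazards to day 28 and no deaths, gives about 35%.

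**Contrast choice.** Exact enumeration for 10/30/30/30, equal true rates of 30-60% in steps of 5 points, each test at 0.05:

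| Family of three tests | Mann-Whitney | Fisher |
|---|---|---|
| Each arm v UC | 9.9-11.4% | 5.0-6.3% |
| Adjacent steps | 12.6-14.0% | 7.0-7.4% |

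The independence formula, 1 − 0.95³ = 14.3%, overstates the comparisons with UC because it ignores the shared control group and the discreteness of the data.

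**Rule for deaths.** Log-rank, 10 v 30, 40% v 70% weaned by day 28, constant competing hazards. In each arm the total cumulative hazard is −ln(1 − weaned − dead), split in proportion to weaned and dead. For 20% deaths in both arms the cumulative death hazards are 0.916 × 0.2/0.6 = 0.305 and 2.303 × 0.2/0.9 = 0.512, a ratio of 1.68. Equal death percentages are therefore not equal death hazards. The other rows follow in the same way.

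| Assumed deaths, UC v active | Death hazard ratio | Significant, deaths censored | Significant, kept as not weaned | Rules disagree |
|---|---|---|---|---|
| 20% v 14% | 1.00 | 40% | 36% | 11% |
| 20% v 20% | 1.68 | 53% | 38% | 18% |
| 30% v 10% | 0.39 | 25% | 34% | 12% |

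With no effect on weaning and equal deaths, both rules give about 5%.

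**The case against.** - **A test is named.** A reader might infer that the plan gives no between-group test for weaning. It does: Mann-Whitney by name, and chi-squared and Fisher through the non-parametric label. What is missing is a test attached to Kaplan-Meier and a statement of which test is primary.
- **Mann-Whitney is not invalid.** On a yes/no outcome with two arms it is nearly the uncorrected chi-squared test, as the arithmetic shows. The problem is its conflict with the other assignments.
- **The study is exploratory.** This stands, and it lowers the need for familywise control. It does not say which analysis is primary, and the plan still declares a primary endpoint and a significance threshold.
- **UC is the control, so the contrasts are implied.** This is a fair reading, but it leaves three comparisons with none designated primary. Section 6.1 adds doubt by describing a control group with electrodes in place and the power off, without saying which arm this is. Because no list of contrasts exists, the familywise figures are conditional. They do not show that the plan will run these tests.
- **The effect of deaths depends on the scenario.** This also stands. A reader might infer a uniformly large effect from the last two rows, but both assume unequal death hazards. With equal hazards the gap is about 4 points.

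**Conclusion.** The concern holds in this form: the plan designates no single primary test, rule for deaths or contrast for weaning, and its text supports conflicting primary results. It should be fixed.

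The choice between Mann-Whitney and Fisher is worth about 12 points of significance at 40% v 70%. Three unadjusted comparisons with UC would put familywise error at about twice the nominal level with Mann-Whitney and close to nominal with Fisher. The rule for deaths is worth about 4 points when death hazards are equal, and 9 to 15 points in either direction when they differ; the two rules disagree in 11-18% of trials.

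The textual conflict rests on no assumption. The sizes rest on assumed weaning and death rates, constant hazards and follow-up to day 28.

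**What to change.** Put the same sentence in the synopsis and section 11, naming one primary analysis of weaning in all randomised patients. Either option reconciles the text:

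- **(a) Proportion weaned** by a fixed day within the scheduled follow-up, deaths counted as not weaned, one named test (for example Fisher's exact), risk difference with 95% CI, and Kaplan-Meier as description. This stays closest to an endpoint called a rate.
- **(b) Time from randomisation to weaning**, compared by log-rank, with patients who die kept as not weaned to the end of follow-up, and the proportion as supportive. This stays closest to the synopsis sentence on methods.

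Under either option:

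1. Delete weaning rate from the Mann-Whitney sentence.
2. Name one primary contrast before data are seen, for example group 4 v group 1, labelled as the package effect because it does not isolate NMES.
3. Report the other contrasts as estimates with 95% CIs and no significance claims, or adjust them by Holm.
4. Reconcile the rules that drop incomplete cases (synopsis item on missing data, section 11.4) with the all-randomised population in section 11.3. Section 4.2 expects 20% not to finish, so the conflict will matter.

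The cost is wording, with no extra patients or measurements, and fewer significance claims. Precision with ten controls stays low: at 40% v 70% the 95% CI half-width is 1.96 × √(0.24/10 + 0.21/30) = 0.345, about 35 points.

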4.3 Schedule of Activities

Time-Event scheme :

Phase	Screening	Treatment	4±1	6~7	Treatment	8~10	11±1	Treatment	13~14	Treatment	15~17	18±1	Treatment	20~21	Follow-up	22~27	28±1	
Day	0-1	1~3	4±1	6~7	8~10	11±1	13~14	15~17	18±1	20~21	22~27	28±1						
In-hospital visit	X	X	X		X	X		X	X	X	X	X	X	X	X	X	X	
Screening/Administrative/Safety																		
ICF/assent form	X																	
Inclusion/Exclusion criteria	X																	
Medical and surgical history, demographics	X																	
Physical exam	X		X				X				X				X			
Vital signs	X	X	X				X				X			X		X		
Height and body weight	X		X				X				X			X		X		
Pulmonary performance (ventilator)	X		X				X				X			X		X		
Laboratory study	X		X				X				X			X		X		
Barthel index	X																	
Echo for diaphragm evaluation	X		X				X				X			X		X		
Randomization/Administration																		
Randomization	X																	
Administration of high protein diet	X	X	X	X	X	X	X	X	X	X	X	X	X	X				
Administration of core muscle rehabilitation	X	X		X	X		X		X		X		X					
Administration of NMES	X	X		X	X		X		X		X		X					
Efficacy/Safety																		
Weaning profile	X		X				X				X	X	X	X		X		
Creatinine clearance rate	X		X				X				X	X	X	X		X		
Weaning rate													X	X				
Length of mechanical ventilator use													X	X		X		
Length of ICU stay													X	X		X		
Length of hospitalization													X	X		X		
In hospital Mortality													X	X				

5. Study Population

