6.2. Concomitant Therapy

Not Applicable

7. Efficacy Assessments

The age, gender, smoking history, diagnosis, length of mechanical ventilator use, APACHE II will be recorded initially.

The pulmonary performance, including tidal volume, maximal inspiratory pressure (MIP), cough function, peak inspiratory pressure (PIP), positive end-expiratory pressure (PEEP), lung compliance, airway resistance, blood gas analysis, Barthel index, serum albumin, creatinine, electrolytes will record before, during (twice per week) and after intervention.

We also follow the outcome of hospitalization, including the weaning rate, mortality, length of mechanical ventilator use, length of ICU stay and total length of hospitalization.

8. Safety Assessments

We will follow serum creatinine level and creatinine clearance rate weekly.

During core muscle rehabilitation and NMES, vital signs (heart rate, blood pressure, respiratory rate) and parameters in ventilator (tidal volume, FiO₂, peak airway pressure) will be monitored.

9. Adverse event reporting

We will report SAEs to the IRB of Chang Gung Medical Foundation according to the Serious Adverse Event Reporting Procedures and Guidelines as posted in the Clinical Trials Resource on the website of Chang Gung Medical Foundation IRB. SAE reports to the IRB should include the following information when calling the Medical Monitor:

- *Date and time of the SAE*
- *Date and time of the SAE report*
- *Name of reporter*
- *Call back phone number*
- *Affiliation/Institution conducting the study*
- *Protocol number*
- *Title of protocol*
- *Description of the SAE, including attribution to drug and expectedness*

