11.3 Analysis Population

All subjects randomized.

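### Section 11.2.1 tests ventilator, ICU and hospital lengths by Mann-Whitney with no rule for patients who die, and the Synopsis names a different method for the same secondary outcomes

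*Combined protocol and SAP*

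**What the plan says.** - **Test.** Section 11.2.1: "Mann Whitney test was used for compare non-parametric data (weaning rate, length of ventilator use, length of ICU stay and length of hospitalization"). The same section says that Kaplan-Meier "survival analysis was performed to assess weaning and survival outcomes"; it does not name ICU or hospital stay there.
- **Synopsis, statistical methods.** "Analyses of primary and secondary outcomes are performed with the use of time-to-event methods according to the intention-to-treat principle". It does not say whether death is censored or treated as a competing event.
- **Population.** Section 11.3: "All subjects randomized".
- **Endpoints.** Section 3.2.2 begins its list with "In hospital mortality, Length of mechanical ventilator usage", followed by ICU and hospital length, albumin and creatinine clearance. Mortality is therefore a separate endpoint, not combined with the lengths. The primary endpoint in Section 3.2.1 has "weaning success defined as weaning from ventilator for 5 consecutive days".
- **Follow-up.** Section 7: "We also follow the outcome of hospitalization, including the weaning rate, mortality, length of mechanical ventilator use, length of ICU stay" and hospital stay. The Section 4.3 schedule ends at day 28±1.
- **Missing data.** The Synopsis omits cases with missing data, and Section 11.4 excludes incomplete clinical data. Neither mentions death.

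No section gives a time origin for the lengths, or says whether days in the respiratory care center (RCC) count as ICU days.

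**The concern.** A length of ventilation or stay ends for two opposite reasons: recovery or death. A rank test on the raw number cannot tell them apart. A patient who dies on day 5 has a length of 5 and ranks ahead of one who weans on day 15. An arm with more early deaths can then look better on a secondary endpoint and be declared significant at 0.05. A late death does the reverse and ranks as a long stay.

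The missing-data rules leave a second route open, in which deaths are removed as incomplete. That compares selected survivors rather than randomised groups. The plan does not choose between the two routes, and the Synopsis offers a third method. The choice could therefore be made after the data are seen.

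**Working it through.** **1. The plan's own figures.** Section 11.1 gives 10 usual-care patients and, on the reading that reaches its total, 30 in each of three other groups: 10 + 3 × 30 = 100, which agrees. No power, effect size, mortality or weaning rate is given, so there is no power figure to reproduce and every rate below is an assumption.

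**2. Direction, by a fixed example.** Take 10 control and 30 active patients with weaning days spread evenly over days 8 to 44 (median 26 in both arms). Let 6 of the 30 active patients die on day 5.
- Raw length: the active median falls to 21.7 days, and the probability that an active patient has the longer length falls from 0.50 to 0.40, which looks like benefit.
- Death ranked worst: the median is 31.0 and the probability 0.60. The direction reverses.

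**3. Model for ventilator days.** Hazards are constant to day 28. The cumulative weaning hazard is Lw = 0.7 in both arms, and the death hazard Ld is solved from

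deaths before weaning = Ld/(Lw + Ld) × (1 − exp(−(Lw + Ld))).

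- 13%: Ld = 0.197; 0.197/0.897 × (1 − exp(−0.897)) = 0.2196 × 0.5922 = 0.130
- 24%: Ld = 0.395; 0.395/1.095 × (1 − exp(−1.095)) = 0.3607 × 0.6655 = 0.240
- 29%: Ld = 0.497; 0.497/1.197 × (1 − exp(−1.197)) = 0.4152 × 0.6979 = 0.290

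Raw days are the day of weaning, death or day 28, whichever comes first. Each setting was simulated (4,000 to 10,000 trials) with a two-sided 0.05 Mann-Whitney test. The table gives the share of trials that significantly favour the deadlier arm (nominal 2.5%).

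| Setting | 13% v 24% | 13% v 29% |
|---|---|---|
| 30 v 30, days from randomisation | about 8% | 13-14% |
| 10 v 30, same | 5-7% | 8-9% |
| 30 v 30, Lw halved or doubled in both arms | 7-10% | 10-17% |
| 30 v 30, adding assumed pre-randomisation days (21 plus exponential, mean 14) | 5.5% | 8.1% |
| 30 v 30, weaning hazard 25% lower in the deadlier arm | 2.9% | 6.4% |

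Repeat runs of the first row gave 8.1-8.7% and 11.6-13.1%. With ventilator-free days to day 28 and death scored 0, the first-row figures become 0-2%. With equal latent mortality, a separate simulation (median weaning time 21 days) gave a two-sided rejection rate of 4.4-5.4% for the raw test, so its level holds.

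**4. Dropping the deaths.** The share weaned by day 28 is Lw/(Lw + Ld) × (1 − exp(−(Lw + Ld))): 0.462, 0.425 and 0.408 at 13%, 24% and 29% deaths. Among those not dead before weaning it is 0.462/0.87 = 53%, 0.425/0.76 = 56% and 0.408/0.71 = 57%. The deadlier arm looks slightly better although the weaning hazards are equal, because slow weaners are exposed to death for longer.

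**5. The Synopsis method.** On one reading (log-rank on weaning, deaths censored), the result disagrees on significance with the Section 11.2.1 test in 9% (13% v 24%) and 13% (13% v 29%) of the same 30 v 30 trials. Censoring deaths also gives a Kaplan-Meier weaning estimate of 1 − exp(−0.7) = 50% in every arm, against the true 46%, 43% and 41%.

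**6. Hospital stay.** With assumed deaths of 10% v 20%, 20% v 30% or 20% v 40% at 30 v 30, reversal is 4-6% if mean time to death is half the mean time to live discharge, 2.4% if the two are equal, and about 1% if it is double. ICU stay was not simulated.

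**The case against.** **The size depends on unverifiable choices.** This stands. Every patient has already been ventilated for more than 21 days (Section 5.1), and ventilator length is recorded initially (Section 7), so "Length of mechanical ventilator use" can be read as total days. Adding those days dilutes the effect. An intervention that raises mortality may also slow weaning; if the deadlier arm's weaning hazard is halved, reversal is 0.8% and 2.0% in the two cases, below nominal.

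**Mortality is reported beside the lengths.** This is a partial safeguard. Reversal together with a non-significant Fisher's test on all deaths to day 28 occurs in 4.5% and 5.0% of 30 v 30 trials in the two cases, against about 2% with equal arms. A reader might push the assumptions to 13% v 48% deaths, where reversal reaches about 49%. The documents support no such gap, and there the mortality test would expose it: the joint figure is 0.9%.

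**All three lengths need not reverse.** A reader might infer that they do. Hospital stay goes above nominal only if deaths come earlier than live discharges. For ICU stay, patients are recruited in the RCC (Section 4.1) and withdrawn on return to the ICU (Section 5.3), which suggests that the RCC is not the ICU. If so, a death in the RCC need not shorten ICU stay.

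**The Synopsis sentence is loose.** It cannot literally cover albumin or creatinine clearance, so to call the two sections flatly incompatible on every outcome goes too far. They still name different methods for ICU and hospital stay and need reconciling.

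**The study is exploratory (Section 11.1).** True, but Sections 11.2 and 11.2.4 still declare significance at 0.05, and with 10 usual-care patients a mortality test has little power.

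**Conclusion.** The omission is certain from the text: three secondary endpoints are compared by ranks in all randomised subjects with no rule for death, and the Synopsis and Section 11.2.1 must be reconciled. Scoring a death by its observed length and dropping it are both biased when mortality differs between arms.

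The size is uncertain and illustrative. For ventilator days at 13% v 24-29% assumed deaths and 30 v 30, false advantage to the deadlier arm is about 8-14% with days from randomisation and equal weaning hazards, about 5-8% with the assumed pre-randomisation days included, and about 3-6% if the deadlier arm weans 25% more slowly. The effect is clearest for ventilator days, conditional for hospital stay and undetermined for ICU stay.

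A reader might infer that the primary endpoint is compromised. It is not, provided that a patient who dies on the ventilator counts as not weaned, which the Section 3.2.1 definition implies. This should be corrected; it does not undermine the trial's main comparison.

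**What to change.** Make one short amendment (Sections 3.2.2, 11.2.1, 11.4 and the Synopsis):
- Reconcile the Synopsis with Section 11.2.1, and count each length from randomisation.
- Name one prespecified death-aware method per length. Examples are ventilator-free days to day 28 with death scored 0, and days to live discharge with in-hospital death ranked worst. A competing-risk analysis would also serve and would fit the Synopsis.
- State whether RCC days count as ICU days.
- Show raw lengths descriptively, with mortality beside them.
- Show weaning as cumulative incidence with death as a competing event.
- State in Section 11.4 that death is an outcome, not missing data.

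**Cost.** IRB review, and day-28 status for withdrawn patients. The outcomes are otherwise already followed, and ventilator-free days need no follow-up past day 28 if weaning not confirmed by then is scored 0. If treatment doubles the weaning hazard and leaves deaths unchanged, ventilator-free days have about 5-6 points less power than raw days at 30 v 30 (41 to 36% at 13% control-arm deaths, 30 to 24% at 29%). The score mixes death and duration, so both components must be shown. Results will be less directly comparable with studies that report raw lengths.
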